WALANT Versus Local Anesthesia in Central Venous Catheter Insertion

Unique Protocol Id: B.30.2.ATA.0.01.00/830

Document Date: 01.11.2023

This was a single-center, prospective, observational study conducted between November 1, 2023, and August 1, 2024. Sixty-four adult patients ( $\geq 18$  years) requiring CVC placement were enrolled. Patients were excluded if they were pregnant, had a Glasgow Coma Scale score  $<15$ , were disoriented, had hemorrhagic shock stage  $>1$ , coagulopathy, local infection, or vascular obstruction. Eligible participants were randomized using a single-blind allocation method based on hospital file numbers: odd numbers received WALANT and even numbers received lidocaine. The WALANT solution was prepared according to the standard protocol and injected into a  $3 \times 3$  cm target area 20 minutes before catheter insertion. CVCs were placed without ultrasound guidance in jugular, subclavian, or femoral veins by anatomical localization. Pain intensity was assessed using the Visual Analog Scale (VAS) before and after the procedure.

For the control group, patients requiring CVCs were selected in the emergency resuscitation room and, unless contraindicated, the procedure was performed without any guidance such as ultrasound, after selecting the catheter insertion site (either the femoral vein, subclavian vein, or jugular vein). After marking the anatomical location, the vein to be used was identified by using a 10cc syringe and applying negative pressure to the skin and subcutaneous tissues. While the needle was slowly withdrawn, local anesthesia was induced with an average of 2-10ml lidocaine (1.5-2 mg/kg) applied to the designated  $3 \times 3$  cm area. CVC insertion was then performed according to routine procedures. Patient assessments were recorded using a visual analog scale before and after the procedure.

Data from the case and control groups were statistically analyzed.

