WALANT Versus Local Anesthesia in Central Venous Catheter Insertion

Unique Protocol Id: B.30.2.ATA.0.01.00/830

Document Date: 01.11.2023

Statistical analyses of the study were performed using the IBM SPSS Statistics for Windows, Version 31.0 (Armonk, NY: IBM Corp) package program. The distributional properties of continuous numerical variables were assessed using visual (histogram and Q–Q plot) and analytical (Shapiro–Wilk test) methods. Comparisons between two independent groups were made for non-normally distributed data using the Mann–Whitney U test, and for normally distributed data using the Independent Samples t-test.

Descriptive statistics for non-normally distributed variables were presented as median, 25%–75% quartiles, and minimum–maximum values, and boxplot plots were used for visual assessment of distribution. Normally distributed data were expressed as mean \pm standard deviation and 95% confidence intervals; error bar graphs were preferred for visual presentation of these variables.

For group comparisons of categorical variables, the Pearson chi-square test or Fisher's exact test was used, depending on the appropriateness of the data. Categorical data were presented as frequency (n) and percentage (%), and were also visualized with bar graphs. In all statistical analyses, a p value of <0.05 was considered statistically significant.

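### Arms were set by odd or even file number, so the study is neither randomized nor observational, and no allocation concealment is described

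*Protocol*

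**What the plan says.** The first paragraph of the Protocol carries two design labels. The opening sentence reads "This was a single-center, prospective, observational study conducted between November 1, 2023, and August 1, 2024". Later in the same paragraph comes the allocation: "Eligible participants were randomized using a single-blind allocation method based on hospital file numbers: odd numbers received WALANT and even numbers received lidocaine". Nothing else is said about how patients were assigned. The paragraph does not say who was blinded, when the file number was issued, or who could see it when eligibility was decided.

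The Protocol also records two items that could serve as baseline information: pain ("Pain intensity was assessed using the Visual Analog Scale (VAS) before and after the procedure") and insertion site, which could be jugular, subclavian or femoral.

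The SAP gives general methods. "Comparisons between two independent groups were made for non-normally distributed data using the" Mann–Whitney test, with the t-test for normal data, Pearson chi-square or Fisher for categorical data, descriptive statistics for each type, and significance at p below 0.05. It names no outcome, baseline variable or covariate.

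**The concern.** The design label tells a reader how far a difference between arms can be attributed to treatment. Calling the study randomized claims a protection that parity of a file number does not give: the arm is fully determined by a number that may exist before anyone decides whether to enrol the patient. Calling it observational errs the other way, since treatment was assigned by rule and not merely recorded. Both labels are wrong for the mechanism described.

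If whoever enrolled patients could read the file number, they could know the arm in advance. Any enrolment decision that depended both on the arm and on expected pain would put part of a VAS difference down to who entered each arm, and the unadjusted tests would then no longer hold their 5% error rate. Because no baseline variable is named for comparison, a reader cannot count on seeing the data that would help to judge this.

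**Working it through.** **Text check.** The labels and the mechanism, side by side:

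| Property | What the Protocol states | What the mechanism gives |
|---|---|---|
| Observational | Opening sentence | Not met: treatment is assigned by rule |
| Randomized | Allocation sentence | Not met: parity is deterministic, with no random sequence |
| Single-blind | Allocation sentence | Blinded party not named; blinding is in any case not concealment |
| Concealment | Not described | Not known whether the file number was hidden until enrolment was decided |

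The main finding rests on this table alone and needs no arithmetic.

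**Illustration of the mechanism.** The only input from the documents is N = 64. The SAP's 0.05 threshold is taken as two-sided, which it does not state. Everything else is assumed: 32 per arm, no true effect, a fraction q of one arm not enrolled because those patients were expected to do worst, and a correlation r between that expectation and VAS.

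Step 1. The shift in mean VAS caused by the selection, in SD units, is

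d = r × φ(z_q) / (1 − q).

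For q = 0.20, z_q = −0.842 and φ(z_q) = 0.280, so φ/(1 − q) = 0.280/0.80 = 0.350. With r = 0.5, d = 0.175.

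Step 2. The noncentrality of the t statistic is d / √(1/32 + 1/32) = 0.175 / 0.25 = 0.70.

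Step 3. The two-sided rejection rate from the noncentral t with 62 degrees of freedom (critical value 1.999) is 10.6%.

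The same steps over the assumed range:

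| Not enrolled, one arm | r = 0 | r = 0.3 | r = 0.5 | r = 0.7 |
|---|---|---|---|---|
| 10% | 5.0% | 5.6% | 6.7% | 8.4% |
| 20% | 5.0% | 7.0% | 10.6% | 16.2% |
| 30% | 5.0% | 9.0% | 16.5% | 27.8% |

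**Sensitivity to the split.** The Protocol does not give arm sizes. If parity behaved like a fair coin, the chance of exactly 32/32 is 0.099 and the central 95% range for one arm is 24 to 40. With 24/40 and r = 0.5 the rates are 6.6%, 10.2% and 15.7% for 10%, 20% and 30% not enrolled, so the split matters little.

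The r = 0 column is as informative as the others: selection unrelated to VAS leaves the error rate unchanged.

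**The case against.** The best defence is that nothing is hidden. The sentence that says randomized also discloses the odd/even rule, so a careful reader can discount the word. Parity may also have produced comparable arms: if enrolment did not depend on the arm, the comparison is informative. The study is described as completed, so the allocation cannot now be changed. All of this stands. It limits the remedy to labelling, reporting and interpretation, but it does not make either label correct.

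A second objection is that the SAP's two-group methods already cover pre-procedure VAS and insertion site by arm. That is right as to method. What is missing is any named variable, so nothing commits the report to showing them.

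Three stronger readings are tempting and are not supported:

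- **That selection by arm took place.** The documents show only that it was possible. The control paragraph's wording, "For the control group, patients requiring CVCs were selected in the emergency resuscitation room", might be read as evidence of selection, but it may mean no more than that patients needing a catheter were identified there. It carries no weight here.
- **That the error rates above measure bias in this study.** Every input except N = 64 is assumed, including removal of expected-worst patients from one arm only. They show a direction and do not bear on how serious the labelling error is.
- **That pre-procedure VAS was taken at different points in the two arms.** WALANT was injected into a "cm target area 20 minutes before catheter insertion", whereas for controls "While the needle was slowly withdrawn, local anesthesia was induced" within the described procedure. A reading before the injection in both arms is equally consistent with the text. The timing needs stating, but it is a separate measurement question and does not affect the allocation finding.

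**Conclusion.** The point holds as a matter of text. The study is called both observational and randomized, and the mechanism described is neither: it is deterministic, quasi-random allocation by file-number parity, with no concealment described and no blinded party named. It should be corrected because it changes what the study can conclude.

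Selection by arm cannot be excluded and has not been shown. No size of bias can be derived from the documents. Under the assumptions stated, a nominal 5% test would run anywhere from 5.0% to 27.8%, with 10.6% at 20% selective non-enrolment and r = 0.5.

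A reader might infer that proof of concealment would rescue the word randomized. It would not: hiding the file number until enrolment was decided would reduce the scope for selection, but the rule would still be deterministic and treatment would still be assigned.

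**What to change.** **Required**

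(a) Replace both design labels with *prospective interventional study with quasi-random allocation by file-number parity*, whether or not concealment can be documented. Add *concealment not described* unless the investigator can document that the file number was hidden until enrolment was decided. State who was blinded.

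(b) Analyse patients by parity, as allocated. Report pre-procedure VAS and insertion site by arm using the descriptive methods already in the SAP, and state when that VAS was taken relative to the anaesthetic injection in each arm. Report screened and excluded counts by parity if a log exists; otherwise say that none exists.

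(c) State in the conclusion that allocation was quasi-random and that selection by arm cannot be excluded, and limit the causal claim to match.

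**Optional, post hoc**

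Adjust post-procedure VAS for pre-procedure VAS as a sensitivity analysis beside the unadjusted test, and only if the pre-procedure reading preceded the injection in both arms. Adjustment addresses measured imbalance only and does not restore randomisation.

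**Cost**

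Wording changes in the Protocol and SAP, one table from data on 64 patients already collected, and one regression if the optional analysis is done. The downside is a weaker design label and a more qualified conclusion.

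### The 20-minute interval is stated for the WALANT arm only and no criterion requires patients of both arms to be able to wait, so selective omission, loss or switching of odd-numbered patients cannot be ruled out

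*Protocol*

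**What the plan says.** The protocol has no numbered sections; the relevant text is its first paragraph and its control-group paragraph.

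- **Allocation.** Patients judged eligible were assigned "based on hospital file numbers: odd numbers received WALANT and even numbers received lidocaine".
- **WALANT arm.** The solution goes into the "target area 20 minutes before catheter insertion".
- **Control arm.** Lidocaine is given as the needle is withdrawn, after which "CVC insertion was then performed according to routine procedures". No interval is stated.
- **Setting.** The control-group paragraph says that "patients requiring CVCs were selected in the emergency resuscitation room". The first paragraph names no location for the WALANT arm.
- **Exclusions that bear on urgency.** Patients are excluded for a Glasgow Coma Scale score below 15, disorientation, or haemorrhagic shock above stage 1. Nothing refers to ability to wait.
- **Numbers and analysis.** "Sixty-four adult patients" were enrolled, with no split by arm. The SAP plans an unadjusted t-test or Mann–Whitney test between two groups at 0.05. Neither document defines an analysis set, a rule for patients who do not get the allocated treatment, or counts of patients allocated, treated and analysed.

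**The concern.** As written, the design makes only one arm tolerate a stated delay. An odd-numbered patient who cannot wait 20 minutes cannot receive WALANT as described. That patient would have to be left out, dropped, switched to lidocaine or treated off schedule. An equally urgent even-numbered patient meets no such obstacle and remains a control.

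The selection need not happen after allocation. Because the file number gives the arm away, an urgent odd-numbered patient might simply never be entered.

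If patients who cannot wait also score pain differently, the arms would differ in urgency, and part of any VAS difference would come from selection rather than from the anaesthetic. The planned comparisons are unadjusted, so nothing in the analysis would correct or reveal this.

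**Working it through.** **Plan's own figure.** The only number is the total of 64. It cannot be reproduced, because no effect size, SD or power is given. For scale, with 32 per arm and two-sided 0.05, the detectable difference is (1.96 + 0.84) × √(2/32) = 0.70 SD at 80% power.

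**Inputs.**
- From the documents: 64 patients; significance level 0.05.
- Assumed: 32 per arm; a two-sided test; a t-test with common SD 1 and no true treatment effect; *f*, the share unable to wait, equal in both arms before selection; *D*, the difference in mean VAS, in SDs, between those who cannot and can wait. The documents give neither *f* nor *D*, so both are run from zero upwards.

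**Dropped from WALANT.** WALANT keeps 32(1 − f) patients, none unable to wait. Controls stay at 32 with share f unable to wait. Bias = f × D.

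**Switched and analysed as treated.** WALANT again keeps 32(1 − f). Controls become 32 + 32f, of whom 64f cannot wait, a share of 64f / (32 + 32f) = 2f/(1 + f). Bias = 2f/(1 + f) × D.

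**False-positive rate.** Noncentral t, with noncentrality bias / √(1/n₁ + 1/n₂) and n₁ + n₂ − 2 degrees of freedom.

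Example, f = 20% and D = 0.75:
- Dropped: bias = 0.20 × 0.75 = 0.15 SD; arms 25.6 and 32; noncentrality 0.15/0.265 = 0.57; false positives 8.6%.
- Switched: bias = (0.40/1.20) × 0.75 = 0.25 SD; arms 25.6 and 38.4; noncentrality 0.25/0.255 = 0.98; false positives 16.2%.

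| f | D (SD) | Dropped: bias (SD), false positives | Switched, as treated: bias (SD), false positives |
|---|---|---|---|
| 0, or any f with D = 0 | – | 0, 5.0% | 0, 5.0% |
| 2% | 0.5 | 0.01, 5.0% | 0.02, 5.1% |
| 5% | 0.5 | 0.025, 5.1% | 0.05, 5.4% |
| 10% | 0.5 | 0.05, 5.4% | 0.09, 6.5% |
| 20% | 0.75 | 0.15, 8.6% | 0.25, 16.2% |
| 30% | 1.0 | 0.30, 18.8% | 0.46, 41.1% |

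The sign of the bias follows the sign of D. Patients left out before enrolment shift the means by the same f × D, although arm sizes would differ somewhat if recruitment continued to 64.

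**The case against.** The strongest reply is that this is a scenario and not an observed fault, and much of that stands.

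- A reader might infer that odd-numbered patients were in fact lost or switched and that the comparison is biased. The documents report no loss, no switch and no patient unable to wait.
- A reader might take the verb in "odd numbers received WALANT and even numbers received lidocaine" as a sign that groups were formed by treatment given. The sentence describes the allocation rule, and on its face allocation and receipt coincide. No as-treated analysis is specified, so the larger figures are only a what-if.
- The urgent setting is written for controls only. Extending it to odd-numbered patients is reasonable, since one eligible pool is split by parity, but it is an inference. That controls do not wait is likewise read from silence.
- The consciousness, orientation and shock exclusions all narrow the pool, so the share unable to wait could be small. At 2–5% and 0.5 SD the error rate barely moves.
- Parity allocation and the undefined analysis set are the deeper weaknesses, and this is one consequence of them.

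None of this removes the asymmetry. A delay is stated for one arm, no criterion equalises it, the arm can be known beforehand, and no counts show that it did no harm.

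**Conclusion.** The concern holds as a risk that the documents leave open, not as a demonstrated bias. Followed as written, the protocol puts a tolerance-of-delay filter on one arm, and neither document supplies a rule, a count or an analysis set to show that the filter had no effect.

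Within the assumed ranges, the effect runs from none to 0.30 SD (false positives 5–19%) if patients are dropped, and from none to 0.46 SD (5–41%) if they are switched and analysed as treated. At 20% unable to wait and a 0.75 SD difference, the bias is 0.15 SD or 0.25 SD, which is roughly a fifth or a third of the 0.70 SD detectable at 80% power. These figures rest wholly on the assumed share, VAS difference and equal arms; if the share or the difference is zero, there is no bias. The direction cannot be determined. The point should be addressed, but it does not by itself invalidate the comparison.

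**What to change.** **Protocol.** Make compatibility with the 20-minute interval that the protocol already states an eligibility condition for both arms, recorded for each candidate before file-number parity is consulted. The investigators should reconcile the timing text of the two arms; how timing is managed clinically is for them to settle.

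**SAP.** Add one line: every enrolled patient is analysed in the arm given by parity, whatever was administered.

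**Patients already enrolled.** The protocol is written in the past tense, so a new criterion may come too late for them. Report the numbers screened, allocated, treated and analysed by parity, with reasons for every omission, loss or switch, and analyse by parity. Allocation can be recovered from the file numbers. If the counts show no selective loss or switching, the concern largely closes.

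**Cost.** One eligibility line, one SAP line and a flow table. The population becomes slightly narrower. If a share f was switched, analysis by parity dilutes a true effect to about (1 − f) of its size, for example 80% at f = 20%. It cannot recover patients never entered or those without a VAS score. The screen also protects only partly while parity stays visible, because the judgement on waiting could itself be influenced by knowing the arm.

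### Three insertion sites are pooled in unadjusted two-group tests although the arm can be known when the site is chosen; tabulate site by arm and add a site-adjusted VAS analysis.

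*Protocol*

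**What the plan says.** **Sites.** The Protocol's first paragraph says that "CVCs were placed without ultrasound guidance in jugular, subclavian, or femoral veins by anatomical localization". It gives no quota, stratification or rule for choosing among the three.

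**Allocation.** The same paragraph says patients were "randomized using a single-blind allocation method based on hospital file numbers", and that "odd numbers received WALANT and even numbers received lidocaine". Who is blinded is not stated. Anyone who can see the file number can work out the arm.

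**Timing of site choice.** The control-group paragraph places the control procedure "after selecting the catheter insertion site (either the femoral vein, subclavian vein, or jugular vein"). That puts site choice before the lidocaine injection, but for patients already described as controls. No matching step is described for the WALANT arm, and neither document says the site is recorded before the arm is known.

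**Outcome and analysis.** The Protocol says that "Pain intensity was assessed using the Visual Analog Scale (VAS) before and after the procedure". The SAP does not name VAS. For continuous variables it says "Comparisons between two independent groups were made for non-normally distributed data using the Mann–Whitney U test", with the independent-samples t-test for normally distributed data. Categorical variables get a chi-square or Fisher test. There is no regression, stratified test, covariate or site subgroup.

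**The concern.** Site is a plausible source of variation in pain, it is known for every patient, and the planned comparison ignores it. Two separate things follow if pain does differ by site.

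- **Bias.** If the choice of vein depends on the arm, the arms have different underlying site mixes, and part of the site difference is read as an anaesthetic effect. The allocation method leaves this open.
- **Precision.** If the underlying mix is the same in both arms, the unadjusted test is valid, but between-site variation stays in the error term and the realised mix still varies by chance.

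What is at stake is whether a VAS difference can be attributed to the anaesthetic technique and, to a lesser degree, how precisely it is estimated.

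**Working it through.** **Inputs from the documents.** Total sample "Sixty-four adult patients"; three sites; significance at p < 0.05. The sample size comes with no effect size, SD or power, so it cannot be reproduced.

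**Assumptions.** 32 per arm (arm sizes are not stated); two-sided testing; within-site SD of 1; site means of 0, 0.5 and 1 (a 1 SD span), or half those values (a 0.5 SD span); site shares as given below. None of the site values comes from the documents.

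**1. Variance due to site (1 SD span).** Between-site variance = sum of share × mean² − (sum of share × mean)².
- Equal thirds: (0 + 0.25 + 1)/3 − 0.5² = 0.167. Share of total variance: 0.167/1.167 = 14%.
- Shares 50/30/20: (0.3 × 0.25 + 0.2 × 1) − 0.35² = 0.1525. Share: 0.1525/1.1525 = 13%.
- At a 0.5 SD span the variance falls to a quarter: 0.167/4 = 0.042, or 4% of the total.

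**2. Chance imbalance, same underlying mix.** SD of the shift in the arm difference = sqrt(2 × between-site variance / 32).
- 1 SD span, equal thirds: sqrt(2 × 0.167/32) = 0.102, so the 95% range is about ±0.20 SD. At a 0.5 SD span it is half that, about ±0.10 SD.
- The unadjusted test already allows for this shift. Simulated with the same mix in both arms, its false-positive rate was 4.2% to 5.0%.
- The cost is power. For a true effect of 0.7 SD at a 1 SD span, simulated power is 72% unadjusted and about 77% with site in the model. At a 0.5 SD span the two are almost equal (77% v 78%, within simulation error).

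**3. Site choice that depends on the arm.** Bias = sum over sites of (difference in share) × site mean. Take shares of 50/30/20 in one arm and 30/30/40 in the other.
- 1 SD span: arm means from site alone are 0.35 and 0.55, so the bias is 0.20 SD. Between-site variances are 0.1525 and 0.1725, so the total SD is sqrt(1 + 0.1625) = 1.078. The standardised shift is 0.20/(1.078 × sqrt(2/32)) = 0.74. The normal approximation to the false-positive rate is P(Z > 1.96 − 0.74) + P(Z < −1.96 − 0.74) = 0.112 + 0.003, or about 11.5%. Simulation with the t-test gives 11.0%, against 5.1% with site in the model.
- 0.5 SD span: the bias is 0.10 SD and the standardised shift is 0.10/(1.020 × 0.25) = 0.39. The rate is 0.058 + 0.009, about 7%. With site in the model it is about 5%.

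**4. Would a test on site mix give enough warning?** A two-group test on one site's share, 45% against 25% at 32 per arm, has only about 39% power. With equal thirds in both arms, chance alone gives a gap of 20 points or more in at least one site in about 19% of trials. A non-significant site-by-arm test would therefore not be reassuring, and a gap of that size would not by itself show that site was chosen by arm.

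**The case against.** The strongest reply is that the bias needs two things the documents do not show: that pain differs by site, and that operators chose the vein according to the arm. Neither VAS by site nor site shares are given, and no reason is offered for preferring one vein under one anaesthetic. That stands. The finding is that the design permits the problem and the analysis does not guard against it.

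A reader might infer that any difference in site mix, including one due to chance, biases the result or inflates the error rate. It does not: with the same underlying mix the planned tests hold about 5%. A reader might also reach for very high error rates. Simulated rates do rise to about 55%, but only with a 40-point shift in shares and a 3-point VAS gap between the extreme sites (within-site SD 2 points). Nothing in the documents points to values that extreme.

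It is also fair to say that site is a secondary matter here. The root weakness is allocation by a visible number. If the site was chosen with the arm known, adjusting for site removes the site-mix part of the bias but not the effect of the patient factors behind the choice, nor selection at enrolment. Recording the site first cannot be fully assured while the file number is in view, and the Protocol's past tense suggests enrolment is over.

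Finally, the SAP's chi-square or Fisher test could already be applied to site by arm. That would describe the mix, but it would not adjust the VAS comparison.

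**Conclusion.** The gap is real and inexpensive to close. Three sites are pooled, the arm is readable before the site is chosen, and the analysis has no site term. How much this matters depends on assumed values. For a 20-point shift in site shares, the false-positive rate is about 7% (0.5 SD span) to about 11% (1 SD span), against about 5% with site in the model. The precision gain runs from almost nothing at 0.5 SD to about five percentage points of power at 1 SD. If pain does not differ by site, there is no bias and the adjustment brings no gain.

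The documents do not support a statement that site was chosen by arm, or that the comparison is in fact confounded. Nor do they support presenting site adjustment as a cure for the allocation method. This is a worthwhile improvement to the analysis, not evidence that the result is wrong.

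**What to change.** In the SAP:

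1. Tabulate insertion site by arm, with counts and percentages.
2. Compare post-procedure VAS with a linear model containing arm and pre-procedure VAS. This presumes the first VAS reading precedes the anaesthetic injection, which the Protocol does not state and the SAP should confirm.
3. Report the same model with site as a three-level factor, next to the unadjusted result. If VAS is clearly non-normal, use a site-stratified rank test such as van Elteren in place of the site-adjusted model.

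In the Protocol, for any patients still to be enrolled, record the intended site before the allocation is known. If enrolment is complete, state in the report that site may have been chosen with the arm known, and that adjustment does not remove bias from the patient factors behind that choice or from predictable allocation at enrolment.

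The cost is about three degrees of freedom: two for site and one for pre-procedure VAS. Residual degrees of freedom fall from 64 − 2 = 62 to 64 − 5 = 59. There is slightly more analysis, and for past patients it requires that the site was recorded.

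### Do the control arm's lidocaine volume and its weight-based dose contradict each other?

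*Protocol*

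**What the plan says.** The Protocol's second paragraph, on the control group, gives the anaesthetic as "an average of 2-10ml lidocaine (1.5-2 mg/kg"), over the marked 3 x 3 cm area. No concentration, body weight or weight limit is given, and nothing says whether volume or mg/kg governs if they differ.

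The first paragraph gives the population as "Sixty-four adult patients" across both arms, with allocation by file number: "odd numbers received WALANT and even numbers received lidocaine". For the other arm it says only that "The WALANT solution was prepared according to the standard protocol".

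The SAP does not mention dose. It sets general rules for describing and comparing continuous and categorical variables.

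**The concern.** The parenthesis reads as if the two ranges were the same dose in different units. The widths do not match: the larger volume is five times the smaller, while the larger mg/kg figure is only a third above the smaller. At 10 or 20 mg/ml, 2 ml is 1.5-2 mg/kg only for someone far lighter than an adult.

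Lidocaine is the only comparator and VAS pain the only outcome the Protocol names, so the point is not trivial. If operators followed the volume and ignored the mg/kg figure, some controls could have been under-dosed, which would raise control pain and flatter WALANT. Light patients given the top volume could have exceeded the mg/kg range, which is a safety matter. The WALANT amount is not stated either, so a reader cannot compare the anaesthetic given in the two arms.

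**Working it through.** **Inputs.** From the Protocol: volume 2-10 ml, dose 1.5-2 mg/kg, adults. Assumed, because neither document gives them: concentration *c* (10, 20 and 40 mg/ml shown) and body weight *w* (40-120 kg). Without *c*, the Protocol's pairing of ml with mg/kg cannot be reproduced as a single figure.

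**Formula.** Volume (ml) = dose (mg/kg) x *w* / *c*.

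**Volume needed for 1.5-2 mg/kg**

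| Weight | c = 10 mg/ml | c = 20 mg/ml | c = 40 mg/ml |
|---|---|---|---|
| 40 kg | 6-8 ml | 3-4 ml | 1.5-2 ml |
| 50 kg | 7.5-10 ml | 3.75-5 ml | 1.88-2.5 ml |
| 70 kg | 10.5-14 ml | 5.25-7 ml | 2.62-3.5 ml |
| 100 kg | 15-20 ml | 7.5-10 ml | 3.75-5 ml |
| 120 kg | 18-24 ml | 9-12 ml | 4.5-6 ml |

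At 20 mg/ml the whole mg/kg range lies inside 2-10 ml for every weight from 40 to 100 kg, and part of it does at 120 kg. At 10 mg/ml the fit is complete at 40 and 50 kg. It is lost above 66.7 kg, because 10 ml is 100 mg and 100 / 1.5 = 66.7.

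**When can one patient satisfy both figures?** Some volume in 2-10 ml meets the mg/kg range if 1.5*w*/*c* is at most 10 and 2*w*/*c* is at least 2, that is, if *c* lies between 0.15*w* and *w*. For 70 kg that is 10.5-70 mg/ml. For all weights from 40 to 120 kg at once it is 0.15 x 120 = 18 to 40 mg/ml.

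**The end-to-end comparison.** If one patient correctly receives 2 ml and another correctly receives 10 ml at the same concentration, their weights differ by at least (10/2) / (2/1.5) = 5 / 1.333 = 3.75-fold. At 10 mg/ml, 2 ml corresponds to 20/2 = 10 kg up to 20/1.5 = 13.3 kg. At 20 mg/ml it corresponds to 20-26.7 kg. So the 2 ml end falls below 1.5 mg/kg for any adult of 40 kg or more at either concentration. This is a contradiction only if correctly dosed patients must reach both ends of the volume range, and the Protocol does not say so.

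**Possible departures if volume alone was followed**
- 70 kg, 2 ml: 20/70 = 0.29 mg/kg at 10 mg/ml, or 40/70 = 0.57 mg/kg at 20 mg/ml. These are 19% and 38% of 1.5.
- 50 kg, 10 ml at 20 mg/ml: 200/50 = 4 mg/kg, twice the stated upper figure.

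The first pair would tend to favour WALANT. The second would tend to favour the control arm.

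**The case for a change.** The strongest case for a change needs no assumed concentration. The two ranges are set side by side as equivalents, yet with 40 kg as the lightest weight at 2 ml, 10 ml implies at least 3.75 x 40 = 150 kg. On that reading the pair cannot describe a single dosing rule in a small adult trial. The WALANT amount is also unstated, and the SAP plans no dose summary, so a VAS difference might reflect technique or simply the amount of anaesthetic.

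Part of this stands. The ranges do not correspond end to end, calling a range an average is loose, and the dose cannot be verified without a concentration. If 10 mg/ml was used, the two figures exclude each other for heavier adults.

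The step to a defect in the plan does not stand. The text can equally be read as a weight-based dose with a generous volume envelope, and an envelope wider than needed is imprecise, not inconsistent. Departures from the mg/kg range require operators to have ignored the figure printed beside the volume, and nothing in either document shows that they did. The Protocol compares two techniques and does not claim equal amounts of anaesthetic. The WALANT reference to a standard preparation is a separate matter that says nothing about whether the control figures agree.

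**Conclusion.** No change to the plan follows. This is missing detail that the study team can fill by stating the concentration and which figure governed, which would reconcile the two ranges in the report. If volumes and weights were recorded, the SAP's existing rules for continuous variables already cover a descriptive table of ml and mg/kg by arm, so no new method is needed.

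The one analytic step that might be suggested, dropping controls whose dose fell outside the mg/kg range, would be worse than leaving the analysis alone. It removes patients after allocation, from one arm only, on the basis of treatment received, and can itself bias the VAS comparison.

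On size: the two figures are fully compatible from 40 to 100 kg at an assumed 20 mg/ml, and incompatible above 66.7 kg at an assumed 10 mg/ml. Off-range dosing is possible but not shown, and the low-end and high-end examples push the comparison in opposite directions, so no direction of bias can be claimed. All of this rests on assumed concentrations and weights. It implies no judgement on which dose is appropriate.
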